[figure not shown]
[figure not shown]

Title: Predicting Pain Response to Transcranial Direct Current Stimulation for Phantom Limb Pain in Limb Amputees.

Protocol: 2015P002525

Date: 06/06/2017

[figure not shown]
II. SPECIFIC AIMS

The specific aims of this experiment are as follows:

Aim 1: To assess the predictors of response to transcranial direct current stimulation (tDCS) in phantom limb pain of subjects with limb amputation. We will explore the aim 1 in an open-label pilot study in which patients will receive active tDCS during 5 daily sessions.

The primary endpoint will evaluate the predictors of pain response to tDCS measured by changes in PLP as indexed by a Visual Analog Scale. The study will require a total of 4 weeks to be completed. The first week, each patient will give daily reports of their pain using a VAS,

accounting for their PLP experience in the past 24hs. This initial baseline week will be followed by five days of treatment and a final 2-week follow-up period without any treatment to examine the lasting effects of the therapy. We will examine whether the following predictors are associated with treatment response: lower or upper limb, bilateral or unilateral and traumatic or non-traumatic amputation, baseline pain, age and gender by building a multivariate model.

IV. SUBJECT SELECTION

In this pilot study, we will recruit 50 subjects with phantom limb pain (PLP) of any etiology (traumatic, vascular disease, diabetic amputees or others). Subjects will need to meet all of the following inclusion criteria and none of the following exclusion criteria:

Inclusion Criteria:

1. Able to provide informed consent to participate in the study.
2. Subject is older than 18 years.
3. 3 months of phantom limb pain (experienced regularly for at least once a week) after the amputated limb has completely healed.*
4. Average pain of at least 4 on a numeric rating scale in the previous week (NRS; ranging from 0 to 10).
5. If the subject is taking any medications, dosages must be stable for at least 2 weeks prior to the enrollment of the study.

*The healing status of the limb will need to be confirmed by the subject's physician or by the physician of the protocol [name] (Co-Investigator).

Exclusion Criteria:

[figure not shown]
1. Pregnancy or trying to become pregnant in the next 2 months.
2. History of alcohol or drug abuse within the past 6 months as self-reported.

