Side Effects Questionnaire for tDCS: At each stimulation session, subjects will complete a questionnaire to evaluate potential adverse effects of tDCS (tingling, burning sensation, headache, neck pain, mood alterations) on a 4-point scale (None, mild, moderate and severe). The subjects will be asked whether they have experienced any side effects in an open-ended manner and they will then be specifically asked about headache, neck pain, scalp pain, scalp burns, tingling, skin redness, sleepiness, trouble concentrating, and acute mood change. If any side effects are reported, the degree of relatedness to the intervention will be assessed on a 5-point scale. This type of adverse events questionnaire has been used frequently in our previous tDCS studies [23], including in patients with phantom limb pain [33].

VI. BIOSTATISTICAL ANALYSIS

Data forms and questionnaires will be coded in a standardized manner, and double-entered into our database. Digital measures/recordings will be similarly tracked in our database and regularly backed up. Analyses will be conducted using standard statistical software such as SAS and Matlab.

Sample size calculation:

This is an open label pilot study, we aim to recruit 50 participants with upper or lower, bilateral or unilateral amputation of any etiology that present chronic phantom limb pain at least in one of the amputated limbs. Given we are planning to build a multivariate regression analysis with up to 5 variables and considering 10 subjects per variable, a sample of 50 subjects would be appropriate for this exploratory analysis. The goal of this study is to provide data to generate further hypothesis regarding whether demographic and clinical factors influence treatment response as to be used for designing a randomized clinical trial (RCT). Therefore the goal of this study is not confirm a priori hypothesis but to provide critical data to design a RCT testing the effects of tDCS in this population of PLP.

Statistical Analysis

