For aim 1: The primary outcome is PLP indexed by VAS. PLP will be analyzed using changes in pain. To analyze these data, we will build a multivariate linear regression model in which the dependent variable will be the Visual Analogue Scale (VAS) for PLP using the following covariates: baseline pain (VAS), amputated limb (upper/lower), etiology of amputation (traumatic/ non traumatic), laterality of amputation (unilateral/bilateral), age, and gender. The first step will be perform a univariate analysis for each one of our predictors using univariate linear regression and obtain the values for the unadjusted b coefficients and 95% confidence intervals (CIs). After that, predictors associated with the outcome at a p level <0.01 will be used to build a multivariate linear regression using a forward stepwise model.

Additional statistical models for secondary outcomes will be developed in an exploratory manner. Therefore, we will not correct P values for multiple comparisons.

References

1. Flor, H., Phantom-limb pain: characteristics, causes, and treatment. *Lancet Neurol*, 2002. 1(3): p. 182-9.
2. Nikolajsen, L. and T. Staehelin Jensen, Phantom limb pain. *Curr Rev Pain*, 2000. 4(2): p. 166-70.
3. Manchikanti, L. and V. Singh, Managing phantom pain. *Pain Physician*, 2004. 7(3): p. 365-75.
4. Birbaumer, N., et al., Effects of regional anesthesia on phantom limb pain are mirrored in changes in cortical reorganization. *J Neurosci*, 1997. 17(14): p. 5503-8.
5. Borsook, D., et al., Acute plasticity in the human somatosensory cortex following amputation. *Neuroreport*, 1998. 9(6): p. 1013-7.
6. Flor, H., et al., Phantom-limb pain as a perceptual correlate of cortical reorganization following arm amputation. *Nature*, 1995. 375(6531): p. 482-4.
7. Grusser, S.M., et al., The relationship of perceptual phenomena and cortical reorganization in upper extremity amputees. *Neuroscience*, 2001. 102(2): p. 263-72.

8. Montoya, P., et al., The cortical somatotopic map and phantom phenomena in subjects with congenital limb atrophy and traumatic amputees with phantom limb pain. *Eur J Neurosci*, 1998. 10(3): p. 1095-102.
9. Ramachandran, V.S., D. Rogers-Ramachandran, and M. Stewart, Perceptual correlates of massive cortical reorganization. *Science*, 1992. 258(5085): p. 1159-60.
10. Davis, K.D., et al., Event-related fMRI of pain: entering a new era in imaging pain. *Neuroreport*, 1998. 9(13): p. 3019-23.

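### The p<0.01 screen of limb, etiology, laterality, age and gender leaves out baseline PLP VAS, so real predictors are more likely than necessary to be dropped

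*Combined protocol and SAP*

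**What the plan says.** Section II (Specific Aims) provides for a week of baseline ratings before treatment: "The first week, each patient will give daily reports of their pain using a VAS". In Section VI, under Statistical Analysis, the model for Aim 1 has six covariates: "baseline pain (VAS), amputated limb (upper/lower), etiology of amputation (traumatic/ non traumatic), laterality of amputation (unilateral/bilateral), age, and gender".

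The same paragraph then sets a two-stage procedure. The first stage is "The first step will be perform a univariate analysis for each one of our predictors using univariate linear regression", reported as unadjusted coefficients with 95% confidence intervals. The second stage is selective: "predictors associated with the outcome at a p level <0.01 will be used to build a multivariate linear regression using a forward stepwise model".

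No sentence forces baseline pain into a model at either stage, and none brings back a predictor that failed the first stage. The paragraph names the outcome in two ways, as change in pain and as the PLP VAS itself, so both readings are checked below.

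Under Sample size calculation, Section VI describes an exploratory pilot meant to inform a later randomized trial.

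**The concern.** The study asks one main question: which factors go with response. The decision on five of the six candidates is taken in regressions that omit baseline PLP VAS, the one candidate that measures the outcome itself before treatment. If baseline pain is correlated with the outcome, leaving it out makes the residual variance of each screening test larger than it need be, and with n fixed at 50 that costs power.

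The second stage does not make this good. Baseline pain enters it only by passing its own p<0.01 test. If it does enter, predictors already lost are not reconsidered. At stake is the list of adjusted predictors handed on to the design of the randomized trial.

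**Working it through.** **Inputs from the plan.** The sample size is n=50 ("we aim to recruit 50 participants with upper or lower, bilateral or unilateral amputation of any etiology"), resting on "multivariate regression analysis with up to 5 variables and considering 10 subjects per variable": 5 × 10 = 50, which reproduces. This rule says nothing about the power of the screen, so there is no stated power to reproduce. The screening level is 0.01, taken as two-sided.

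**Assumptions, because the documents give no figures.** Effect d = 0.8 SD of post-treatment VAS; baseline-to-post correlation ρ = 0.5, range 0.3 to 0.7; binary predictor split 25/25 and unrelated to baseline; no dropout; r = baseline SD ÷ post SD, first set to 1.

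**Formulas.** With post-treatment SD = 1, the residual variance V is:
- post VAS, unadjusted: 1
- change, unadjusted: 1 + r² − 2ρr, which is 2(1 − ρ) when r = 1
- either outcome with baseline in the model: 1 − ρ²

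Once baseline is in the model, the predictor's coefficient and p value are the same for change and for post VAS, so the adjusted column below serves both readings.

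Noncentrality = d × √(n × f × (1 − f)) ÷ √V, where f is the share in one group. Power is from the noncentral t with 48 df unadjusted (critical value 2.682) or 47 df adjusted (2.685).

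**Central case, ρ = 0.5, r = 1.** V is 1 unadjusted under either outcome and 0.75 adjusted.
- Unadjusted: 0.8 × √12.5 ÷ 1 = 2.83, power 56%.
- Adjusted: 0.8 × √12.5 ÷ √0.75 = 3.27, power 72%.

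**Range over ρ, r = 1 (chance of passing p<0.01).**

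| ρ | Change, unadjusted | Post VAS, unadjusted | With baseline | Gain, change | Gain, post VAS |
|---|---|---|---|---|---|
| 0.3 | 39% | 56% | 61% | 22 | 5 |
| 0.5 | 56% | 56% | 72% | 16 | 16 |
| 0.7 | 83% | 56% | 89% | 6 | 33 |

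At ρ = 0.5, other effects give 30% to 42% (0.6 SD) and 80% to 91% (1.0 SD). A 10/40 split at 0.8 SD gives 35% to 48%.

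**Unequal SDs, r = 0.7 (change outcome).** V for unadjusted change is 1 + 0.49 − 1.4ρ, that is 1.07, 0.79 and 0.51 at ρ = 0.3, 0.5 and 0.7. The adjusted values are 0.91, 0.75 and 0.51.

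| ρ | Change, unadjusted | With baseline | Gain |
|---|---|---|---|
| 0.3 | 52.6% | 61.2% | about 9 |
| 0.5 | 69.0% | 71.7% | about 3 |
| 0.7 | 89.4% | 89.3% | 0 |

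At ρ = r = 0.7 baseline is uncorrelated with change (0.7 × 0.7 − 0.49 = 0), so there is nothing to gain. The post-VAS figures do not depend on r.

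**Does baseline pass its own screen?** By simulation with r = 1 and no other effect, it passes against change in about 98%, 89% and 59% of trials at ρ = 0.3, 0.5 and 0.7. Against post VAS it passes in about 33%, 89% and 100%.

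**Groups that differ at baseline (ρ = 0.5, r = 1, simulation).** With a 0.8 SD baseline difference:
- A predictor with no effect given baseline passes the unadjusted screen in about 11% of trials, against a nominal 1%.
- A predictor whose groups have equal mean change passes the adjusted screen in about 13%, against about 1% for unadjusted change.

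At a 0.5 SD difference the two inflated rates are about 4% and 5%.

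**The case against.** **The gain rests on equal SDs.** Inclusion criterion 4 in Section IV requires average pain of at least 4 out of 10, which may narrow the baseline distribution while post-treatment pain can fall to 0. This stands: for the change outcome the gain can be small or nil, as the second table shows. It does not touch the post-VAS reading, and the ratio of 0.7 is itself an assumption.

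**Adjustment is not simply less biased.** A reader might infer that the unadjusted screen lets in false predictors and that adding baseline cures this. The documents do not support that. The predictors are not randomized, and Section II defines response as change in PLP, so equal mean change is a legitimate null. Under that null it is the adjusted screen that passes too often. The two analyses answer different questions when groups differ at baseline.

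**The threshold matters more.** At 0.8 SD, ρ = 0.5 and equal SDs, relaxing the cut-off to 0.05 alone gives 79%, adjustment alone 72%, and both 89%. This stands as a separate problem, which adding baseline leaves in place.

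**The study is exploratory, and every predictor's unadjusted estimate is obtained anyway.** This lowers the stakes. A screened-out factor is lost from the multivariate model but its unadjusted coefficient remains. Still, a hypothesis-generating study gains nothing by dropping candidates for want of a covariate it already holds.

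**Conclusion.** The point holds as a loss of precision and as a gap in the specification. Five predictors are judged without the collected baseline value, and nothing guarantees that any model will contain it.

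The central size is 56% against 72%, for a 0.8 SD effect, ρ = 0.5, an even split unrelated to baseline, and equal SDs. Across the assumptions tried at 0.8 SD with an even split, the gain runs from 0 points (change, ρ = 0.7, SD ratio 0.7) to 33 points (post VAS, ρ = 0.7). None of these inputs is in the documents.

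A reader might go further and conclude that real predictors will be discarded. That is too strong: they are more likely than necessary to be dropped, by an amount that cannot be fixed from the plan.

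**What to change.** In Section VI, Statistical Analysis, Aim 1:
- Screen limb, etiology, laterality, age and gender each in a two-term regression with baseline PLP VAS, and apply the p<0.01 rule to the predictor term.
- Keep baseline PLP VAS in the multivariate model whatever its own p value.
- Report the planned unadjusted coefficients and intervals beside the adjusted ones for every predictor. State that they can differ in either direction where groups differ in baseline pain.

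The cost is wording: no new data and no further patients. Each screening model loses one degree of freedom (critical t 2.682 to 2.685). The screened coefficient becomes an association at equal baseline pain and no longer a raw difference, and the SAP should say so. Baseline pain is already on the plan's covariate list, so no new variable is introduced. The power cost of the p<0.01 cut-off needs its own decision.

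### With 50 subjects, the univariate p<0.01 screen and stepwise step overstate the adjusted slopes of weaker predictors that they keep; fitting the six listed covariates together avoids this

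*Combined protocol and SAP*

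**What the plan says.** Section II (Specific Aims) ends its list of six candidate predictors with "baseline pain, age and gender by building a multivariate model". In Section VI, Statistical Analysis, the Aim 1 paragraph describes a multivariable linear model for phantom limb pain "using the following covariates: baseline pain (VAS), amputated limb (upper/lower), etiology of amputation (traumatic/ non traumatic), laterality of amputation (unilateral/bilateral), age, and gender".

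The same paragraph then sets out two steps. In the first, every one of the six predictors is fitted alone and its unadjusted slope and 95% CI are obtained. The second step is selective: "predictors associated with the outcome at a p level <0.01 will be used to build a multivariate linear regression using a forward stepwise model". No entry or stay level is given for the stepwise step, and no shrinkage, bootstrap or other allowance for selection is planned.

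Section VI, Sample size calculation, justifies 50 subjects as follows: "we are planning to build a multivariate regression analysis with up to 5 variables and considering 10 subjects per variable". On purpose it says: "The goal of this study is to provide data to generate further hypothesis regarding whether demographic and clinical factors influence treatment response". The results are meant to help design a randomized trial.

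**The concern.** The plan lists six covariates for one model and then lets the data decide which of them receive an adjusted estimate. A strict threshold in a small sample works as a truncation: a modest true association can pass only in samples that happen to exaggerate it. The slope is then reported from the same data, with an ordinary confidence interval that takes no account of how the predictor was chosen.

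What is at stake is the adjusted information passed to the later trial. A weaker predictor that survives looks more important than it is. One that fails has no adjusted estimate, only an unadjusted slope, which may be distorted if the factor is related to age or baseline pain.

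**Working it through.** **Plan's own figure.** 5 variables × 10 subjects = 50, which reproduces. The plan gives no effect size, SD, power or dropout, so the effects below are assumptions.

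**What the screen demands.** With n = 50 and one predictor there are 48 residual df. The two-sided 1% critical value is t = 2.682, so the smallest observed correlation that passes is

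|r| = 2.682 / √(48 + 2.682²) = 0.361, or R² = 13.0%.

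This step uses only the planned n and the stated threshold (taken as two-sided).

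**One predictor, screen only.** 200,000 simulated bivariate normal trials for each true r:

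| True r | Passes | Mean passing slope ÷ truth | 95% CI coverage if passed |
|---|---|---|---|
| 0.20 | 12% | 2.1 | 78% |
| 0.25 | 20% | 1.7 | 88% |
| 0.30 | 33% | 1.5 | 92% |
| 0.40 | 63% | 1.18 | – |
| 0.50 | 89% | 1.05 | – |

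**Whole procedure against the six-covariate model.** Assumptions: n = 50; six underlying normal variables with common correlation 0, 0.15 or 0.3; three cut at the median (25/25 expected), one at the 80th percentile (10/40 expected), age and baseline pain continuous; outcome = 0.6 × one 25/25 factor + 0.3 × age + slope × baseline pain + N(0,1); baseline slope −0.5, 0, 0.35 or 0.5; stepwise entry at p<0.05. That makes 12 combinations, with 6,000 trials each.

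To place these on the r scale at correlation 0 and slope 0.5: a 25/25 factor has SD 0.5, so 0.6 × 0.5 = 0.30. The outcome variance is 0.09 + 0.09 + 0.25 + 1 = 1.43, with SD 1.196. The factor and age each have r = 0.30/1.196 = 0.25, and baseline pain has r = 0.50/1.196 = 0.42.

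| Correlation / baseline slope | Empty model | At most one predictor | Factor kept | Mean kept factor slope (truth 0.6) | Unadjusted factor slope (coverage) |
|---|---|---|---|---|---|
| 0 / 0.5 | 18% | 73% | 20% | 0.95 | 0.60 (95%) |
| 0.15 / 0.5 | 7% | 47% | 35% | 0.92 | 0.79 (91%) |
| 0.3 / 0.5 | 2% | 28% | 45% | 0.90 | 0.98 (80%) |
| 0.3 / −0.5 | 49% | 93% | 14% | 0.98 | 0.51 (94%) |

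- *Factor.* Over all 12 combinations the kept slope averages 0.90 to 0.98, which is 1.5 to 1.6 times the truth, with coverage of 86–91%. With entry at p<0.15 it averages 0.93 (correlation 0) or 0.82 (correlation 0.3).
- *Age.* When kept, its slope is about 1.5–1.6 times too large in the four combinations tabulated.
- *Baseline pain.* At a slope of ±0.5 it is the predictor kept most often: about 70% of trials at 0/0.5, 86% at 0.3/0.5 and 31% at 0.3/−0.5. Its slope is inflated only about 1.02 to 1.17 times.
- *Larger effects.* With the factor and age effects doubled (1.2 and 0.6; baseline slope 0.5), the factor's inflation is 5% (correlation 0) or 3% (correlation 0.3).
- *Six-covariate model.* In all 12 combinations the factor slope averages 0.60, coverage is 95%, and the CI half-width is 0.60–0.65 SD.

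**Check of the unadjusted bias at correlation 0.3.** Between the two halves of a median split, each correlated covariate differs in mean by 2 × 0.3 × √(2/π) = 0.479 SD. The unadjusted slope is therefore 0.6 + 0.479 × (0.3 + 0.5) = 0.98, or 0.6 + 0.479 × (0.3 − 0.5) = 0.50, in line with the simulated 0.98 and 0.51.

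**The case against.** The best defence is that the study is openly hypothesis-generating. It asks whether factors influence response, not by how much, and nowhere says that the slopes will serve as effect sizes for the later trial. A strict screen that produces few leads is defensible for that purpose. Unadjusted slopes and CIs are obtained for all six predictors before any selection, and they are adequate if the predictors are unrelated. The six-covariate model also breaks the plan's own rule of 10 subjects per variable and gives wide intervals.

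Much of this stands. It makes the point a modest one and rules out saying that the study fails its purpose. It does not remove the point: inflated adjusted slopes with overconfident intervals are poor material even for planning, and the unadjusted slopes are least reliable when predictors are correlated, which is when adjustment is needed.

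Three stronger readings should be resisted.

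- A reader might infer that the adjusted estimates as a whole will be about 1.5 times too large. They will not: that figure belongs to predictors with a true r near 0.30, and a moderate baseline-pain effect, the slope most likely to be kept, is barely inflated.
- A reader might infer that the final model will usually be empty or hold a single predictor. The documents cannot settle this: the empty-model rate ran from 2% to 49% across the combinations tabulated, depending on unknown correlations and signs.
- A reader might see an error in six covariates against a sample size built on five variables. Five can be read as a ceiling on the final model, so the text is not contradictory as it stands.

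**Conclusion.** The concern holds for weaker predictors. At n = 50, those with a true r of about 0.30 or less are mostly screened out and, when kept, have adjusted slopes overstated by about 1.5 times (r = 0.30) to 2.1 times (r = 0.20), with CIs that ignore the selection. At r of 0.40 and above the effect is small.

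The 0.361 threshold and the direction of the bias follow from the plan itself. Its size in this trial rests on assumed effect sizes, correlations, binary splits and stepwise entry level. With correlated predictors, part of the excess in a kept slope comes from related covariates being left out, so the ratios in the whole-procedure simulation are not due to the threshold alone.

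This is a cheap improvement to an exploratory analysis, not a flaw that defeats it.

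**What to change.** In Section VI, Statistical Analysis, Aim 1, remove the p<0.01 screen and the forward stepwise step. Suggested wording: *One linear regression model will include all six listed covariates. All six adjusted coefficients will be reported with 95% CIs whatever their p values, as estimates and not as significance tests. The univariate results will be presented as descriptive.*

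In Section VI, Sample size calculation, change the five-variable figure to six and state that 50 subjects give 50/6 = 8.3 per variable, with 50 − 7 = 43 residual df.

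No new data or patients are needed. The costs should be stated openly:

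- 8.3 subjects per variable is below the plan's own rule, which would need 60 subjects for six.
- Intervals are wide: half-width about 0.60–0.65 SD for a 25/25 factor and about 0.78–0.81 SD for an assumed 10/40 factor.
- There are more chance leads. At least one of three null factors reaches p<0.05 in about 13–14% of trials, against about 2–10% in which the present procedure keeps one.
- The inflation returns if readers pick out only coefficients with p<0.05. The 0.6 SD factor reaches that level in 46–50% of trials and then averages 0.84–0.88, or 1.4–1.5 times the truth. All six must therefore be shown together.

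A lesser change would keep the present procedure, label its slopes as subject to selection, and show the six-covariate model beside it. That discloses the bias but leaves it in the main result.
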